### 4.2 RECRUITMENT

This study will be conducted at up to 6 sites. The study centers will enroll up to approximately 20 patients for Part 1 and up to approximately 40 additional patients for Part 2 of this study.

## 4.3 INCLUSION CRITERIA

Patients eligible for inclusion in this trial must fulfill all of the following criteria:

- 1. Provide signed and dated informed consent prior to initiation of any study-related procedures that are not considered Standard of Care (SOC).
- 2. Male or female patients aged  $\geq$  18 years.
- 3. Have either of the following diagnoses:
  - Morphologically confirmed AML (except acute promyelocytic leukemia (APL)) including leukemia secondary to prior therapy (e.g., chemotherapy, XRT) or antecedent hematologic disorder (e.g., MDS or myeloproliferative disorders), who have failed to achieve complete remission (CR) or who have relapsed after prior therapy and are not candidates for potentially curative therapy.
  - Intermediate-2 or High-grade risk MDS (including chronic myelomonocytic leukemia (CMML)).
- 4. Have received at least one prior therapy. Patients who are over age 65 and have not received therapy for AML are also eligible, if they are not candidates for induction chemotherapy.
- 5. ECOG performance status of 0 (fully active, able to carry out all pre-disease activities without restriction) to 2 (ambulatory and capable of all self-care but unable to carry out

any work activities. Up and about more than 50% of waking hours), measured within 72 hours before the start of treatment.

- 6. Predicted life expectancy of  $\geq$  3 months.
- 7. Adequate renal function [creatinine  $\leq$  1.5 times ULN (upper limit of normal)] or GFR of  $\geq$  50mL/min.
- 8. Adequate hepatic function [total bilirubin  $\leq 1.5 \times \text{UNL}$ ; AST (aspartate transaminase) or ALT (alanine transaminase)  $\leq 3 \times \text{UNL}$  or  $\leq 5 \times \text{UNL}$  if due to liver involvement by tumor].
- 9. Adequate cardiac function,  $\geq$  institutional lower limit of normal, e.g., left ventricular ejection fraction (LVEF) of  $\geq$  50% as assessed by multi-gated acquisition (MUGA) or ultrasound/echocardiography (ECHO); corrected QT interval (QTc) < 470 ms.
- 10. Contraception:
  - For women: Negative pregnancy test for females of child-bearing potential; must be surgically sterile, postmenopausal (defined as no menstrual cycle for at least 12 consecutive months), or compliant with an acceptable contraceptive regimen (oral contraceptives, condom with spermicide etc.) during and for 3 months after the treatment period. Abstinence is not considered an adequate contraceptive regimen.
  - For men: Must be surgically sterile, or compliant with a contraceptive regimen (as above) during and for 3 months after the treatment period.
- 11. Willing and able to participate in the trial and comply with all trial requirements.

#### 12. For Part 2 Group 1 of the Study ONLY:

Positive for RAS mutation at a Clinical Laboratory Improvement Amendments (CLIA)certified laboratory prior to study entry.

## 4.4 EXCLUSION CRITERIA

Patients who fulfill 1 or more of the following criteria will not be eligible for inclusion in this trial:

- 1. Concomitant malignancies except carcinoma in situ, basal or squamous cell skin carcinoma; low grade prostate cancer treated with prostatectomy more than 10 years ago; early stage melanoma treated with complete surgical excision more than 5 years ago; carcinoma in situ of cervix treated with cone procedure more than 8 years ago.
- 2. Gastrointestinal (GI) condition that could impair absorption of study medication (specific cases e.g., remote history of GI surgery, may be enrolled after discussion with the medical monitor), or inability to ingest study medication. Refractory nausea and vomiting must also be discussed with the Medical Monitor prior to enrolling such a patient.
- 3. Uncontrolled or severe intercurrent medical condition.
- 4. Patients with rapidly increasing peripheral blood blast counts (significant increase in the absolute peripheral blast count with white blood cell (WBC) count > 30,000) or uncontrolled (absolute blast count > 30,000) while on hydroxyurea will be excluded.
- 5. Known uncontrolled central nervous system (CNS) involvement. (Stable asymptomatic CNS involvement either untreated or being treated with a stable dose (or doses) of intra-

thecal (IT) therapy can be allowed if there is evidence that the cerebrospinal fluid (CSF) cell count is decreased and that patient is responding to IT therapy.)

- 6. Any cancer-directed therapy (chemotherapy, radiotherapy, hormonal therapy, biologic or immunotherapy, etc.) within 28 days or 5 half-lives, (whichever is shorter).
- 7. Any concurrent or prior use of an investigational drug (including MEK inhibitors) within 28 days or 5 half-lives (whichever is shorter) prior to the first dose of BVD-523. A minimum of 10 days between termination of the investigational drug and administration of BVD-523 is required. In addition, any drug-related toxicity except alopecia should have recovered to Grade 1 or less.
- 8. Received chemotherapy regimens with delayed toxicity within the last four weeks (six weeks for prior nitrosourea or mitomycin C). Received chemotherapy regimens given continuously or on a weekly basis with limited potential for delayed toxicity within the last two weeks.
- 9. Ongoing anticoagulant therapy that cannot be held to permit bone marrow sampling. Patients who require anticoagulant therapy and cannot be maintained on LMWH should not be considered for this study.
- 10. Major surgery within 4 weeks prior to first dose.
- 11. Pregnant or breast-feeding women.
- 12. Any evidence of serious active infections (subjects who have been fever-free for 24 hours prior to enrollment and on active treatment would not be considered excluded).
- 13. Any important medical illness or abnormal laboratory finding that would increase the risk of participating in this study (based on the investigator's judgment).
- 14. A history or current evidence/risk of retinal vein occlusion (RVO) or central serous retinopathy (CSR).
- 15. Concurrent therapy with drugs known to be strong inhibitors of CYP1A2, CYP2D6 and CYP3A4, or strong inducers of CYP3A4 (for list of non-permitted drugs, see Appendix 1).

# 5 STUDY PLAN AND PROCEDURES

This clinical study will consist of 2 parts. In Part 1, patients with AML or MDS will receive sequentially higher oral doses of BVD-523.

Upon completion of Part 1 of this study and determination of RP2D, up to approximately 40 additional AML or MDS patients with and without RAS mutation will be treated at the RP2D.

To characterize the pharmacokinetic properties of BVD-523 in patients with AML or MDS, blood will be obtained/analyzed during Cycle 1 of Part 1, and during additional cycles in Part 1 and/or Part 2 as needed, to measure BVD-523 and selected metabolite concentration levels.

Multiple pharmacodynamics biomarkers will be used to measure response to drug treatment, including evaluation of pRSK and total RSK. Additional biomarkers, including peripheral blood mononuclear cells (PBMCs), and DNA sequence analysis may be identified and measured as appropriate by collection of whole blood prior to dosing initiation and after drug levels have reached steady-state. Leukemic cell genotyping by DNA analysis will be performed to identify somatic alterations, relying on either available archived or freshly collected samples. Blood and/or bone marrow aspirate will be collected to determine *ex vivo* BVD-523 sensitivity on leukemic cells prior to therapy on Day 1 and Day 22.

All patients will be screened and eligibility determined prior to enrollment and start of study treatment.

# 5.1 STUDY PATIENT NUMBER

In Part 1, up to approximately 20 patients are expected to be enrolled.

In Part 2 of the study, up to approximately 40 patients with measurable disease will be enrolled:

- Group 1: patients with RAS mutant positive AML or MDS; n (evaluable)  $\leq 20$
- Group 2: patients with RAS mutant negative AML or MDS; n (evaluable  $\leq 20$

# 5.2 DESCRIPTION OF STUDY VISITS FOR PART 1

Procedures performed in the first cycle are specified in Table 6.3 (Part 1: Schedule of Assessments and Procedures). Patients receiving multiple cycles of treatment will not have blood drawn for PK and PD measurements after Cycle 1 (Day 1 and Day 22) unless additional PK and PD data are deemed necessary after initial analysis.

## 5.2.1 Visit 1 (Day -28 to -1); Screening

The following procedures will be performed at Visit 1 (Screening):

• Obtain written informed consent (before start of any study-related procedures that are not considered Standard of Care) including optional consents for additional future analyses (Note: informed consent may be obtained up to -28 days to allow flexibility in scheduling of the screening procedures).

- Evaluate all inclusion and exclusion criteria to ensure that patients meet all inclusion criteria and none of the exclusion criteria.
- Review medical history including all previous cancer treatments.
- Record prior and concomitant medications including start/stop dates, indication, dose and frequency taken within 30 days of Cycle 1, Day 1.
- Record demographic data including date of birth, age, gender, race, and smoking status. Where full DOB is collected, initials will not be used.
- Measure and record height in cm and weight in kg.
- Perform and record physical examination.
- Assess and record performance status (ECOG) within 72 hours before start of treatment.
- Record vital signs. Measure body temperature, systolic / diastolic blood pressure (BP) and pulse rate.
- Collect blood for a serum pregnancy test for female patients who are not postmenopausal or surgically sterile. If positive, repeat and confirm results prior to Visit 2. A second positive test will result in exclusion of the patient from the study.
- Assess and record current disease status within 28 days.
- Bone marrow aspirate and/or biopsy within 28 days of Visit 1. Peripheral, Geimsa and Iron stained slides will be collected with each bone marrow aspirate or biopsy. Bone marrow aspirate and/or biopsy slides will not be shipped to a third party. As such, the site may utilize BM aspirates performed in clinical practice as SOC, as long as they are collected within the screening window (-28 days).
- Bone marrow cytogenetics in accordance with local pathology requirements. (Cytogenetics would preferably include at least 20 clones).
- Collect blood samples for blood chemistries, hematology and calculated creatinine clearance within 72 hours before start of treatment, analyze, review and report any clinically significant abnormalities to Medical Monitor before dosing.
- Perform and record ophthalmology examination.
- Obtain a 12-lead electrocardiogram (ECG), and echocardiogram (ECHO) or multi-gated acquisition (MUGA) for left ventricular ejection fraction (LVEF).
- Collect urine samples for urinalysis within 72 hours before start of treatment.
- For patients enrolled in Part 2 of this study, bone marrow sample and/or peripheral blood samples will also be required to obtain necessary RAS genetic information.
- Complete Screening/Enrollment Form and submit to Medical Monitor for review prior to treatment of patient.

## 5.2.2 Visit 2 (Day 1 ± 0); Baseline/Drug Dispensing/Initiation of Treatment

The following procedures will be performed at Visit 2 (Baseline):

- Review Screening/Enrollment Form to confirm consent to enroll obtained from Medical Monitor or Sponsor.
- Review all inclusion and exclusion criteria to ensure that patients meet all inclusion criteria and none of the exclusion criteria.
- Review medical history for any changes since Screening Visit.

- Record medications including start/stop dates, indication, dose and frequency for any changes since Screening Visit.
- Perform and record physical examination.
- Measure and record weight in kg.
- Assess and record performance status (ECOG) if not done during Screening Visit within 72 hours of start of treatment.
- Record vital signs (body temperature, systolic / diastolic BP and pulse rate).
- ONLY if the screening pregnancy test was performed more than 1 day previously, collect blood for a repeat serum pregnancy test for female patients who are not postmenopausal or surgically sterile.
- Collect pre-dose blood samples for pharmacokinetic (PK), pharmacodynamic (PD), and PBMC analyses.
- Collect pre-dose blood samples for blood chemistries, hematology and creatinine clearance if not done during Screening Visit within 72 hours of start of treatment.
- Collect pre-dose urine samples for urinalysis.
- Administer first dose of BVD-523.
- Collect post-dose blood samples for pharmacokinetic (PK), pharmacodynamic (PD), and PBMC analyses.
- Assess and record adverse events (AEs).
- Dispense study drug and instruct patients how to take study drug, daily every 12 hours ± 2 hours with at least 8 ounces of water on an empty stomach, i.e., fasting (30-60 minutes before food or 2 hours after food).
- Inform patients of the potential photosensitizing effects of BVD-523 and instruct them to avoid sunlight and wear protective clothes, sunglasses, and apply sunblock when outside, including when driving a car.

### 5.2.3 Visit 3 (Day 8 ± 1)

The following procedures will be performed at Visit 3 (Day 8):

- Review medical history.
- Record concomitant medications including start/stop dates, indication, dose and frequency taken after Visit 2.
- Perform and record targeted physical examination as appropriate.
- Assess and record performance status (ECOG).
- Record vital signs. Measure body temperature, systolic / diastolic BP and pulse rate.
- Collect blood samples for blood chemistries, hematology and creatinine clearance.
- Collect urine samples for urinalysis.
- Dispense drug supply for self-dosing, and remind patients of dosing instructions.
- Obtain all unused study drug from patient.
- Assess study drug compliance by pill count.
- Obtain a 12-lead ECG.
- Assess and record AEs.

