### **QTc Prolongation**

The balance of preclinical evidence suggests BVD-523 has low, but observable, potential to cause QT prolongation. Due to potentially unique species sensitivity, as well as possibly unknown consequences following chronic dosing, patients dosed with BVD-523 in the first-in-human study, BVD-523-01, are being monitored for potential QTc prolongation and related cardiotoxicities via Holter monitoring. No clinically significant cardiac abnormalities have been seen to date in the first trial (BVD-523-01). QTc assessment will be performed at baseline and on Day 8, at steady state.

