### 1.5.3 Toxicity and Safety Studies

When BVD-523 was characterized using *in vitro* screens against 66 receptors and ion channels, no toxicologically significant interactions were identified. Additionally, BVD-523 was negative in bacterial mutation and *in vivo* micronucleus screening assays; therefore, BVD-523 is not considered to have a significant genetic toxicology risk.

While BVD-523 modestly inhibits the human ether-a-go-go related gene (hERG) current (IC50 3.4  $\mu$ M), no significant effects were seen in action potentials recorded from dog Purkinje fibers exposed to up to 10  $\mu$ g/mL and no significant cardiovascular findings were observed upon acute oral dosing of the compound at dose levels up to 50 mg/kg in dogs (Cmax = 17.3  $\mu$ M). Thus BVD-523 is considered to have a low potential to cause QT prolongation in patients, but, as stated, the first-in-human study will monitor for signs of cardiovascular effects of BVD-523 in humans.

No significant cytochrome P450 (CYP) inhibition has been observed with the compound.

*In vitro* studies suggest that the compound is metabolized primarily via oxidation by multiple CYPs including 3A4, 2D6, and 1A2. Furthermore, no significant CYP induction was observed after up to 14 days drug treatment in rats, nor during *in vitro* studies with human hepatocytes. These data suggest a limited potential for drug-drug interactions.

BVD-523 HCl salt is orally available in multiple species (absolute bioavailability %F = 23% in dog to 100 % in monkey) when formulated as a simple suspension in 1% carboxymethyl-cellulose (CMC) and has a half-life of 2-4 hours across all species.

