## 6.5 SAFETY ASSESSMENTS

Safety evaluations will be conducted at baseline, on Days 1, 8, 15, 22, 29, 36, 43, and, in patients who continue treatment, every 3 weeks or if clinically indicated thereafter. These evaluations will include a targeted physical examination, electrocardiography in subjects where clinically indicated and clinical laboratory studies. An ophthalmologic assessment will be conducted at baseline, at the end of study and at other visits by an ophthalmologist if clinically indicated.

The following clinical laboratory tests will be performed:

- **Hematology** (blood sample: EDTA) hemoglobin, hematocrit, white blood cells (WBC) count with differential, red blood cells (RBC) count, and platelet count.
- **Blood Chemistry** (blood sample: serum) albumin, alkaline phosphatase (ALP), total bilirubin, calcium, chloride, creatinine, glucose, inorganic phosphorus, potassium, total protein, alanine aminotransferase (ALT), aspartate aminotransferase (AST), sodium, blood urea nitrogen (BUN) uric acid, cholesterol and triglycerides (at screening and first day of Cycle 1).
- If the total bilirubin concentration is increased above 1.5 times the upper normal limit, total bilirubin should be differentiated into the direct and indirect reacting bilirubin.
- Urinalysis specific gravity, pH; semi-quantitative "dipstick" evaluation of glucose, protein, bilirubin, ketones, leukocytes, and blood and a microscopic examination including RBC, WBC and casts will be performed if the dipstick is abnormal.

Blood chemistry will be analyzed at each trial center by a certified laboratory and a report of the laboratory values will be sent to the trial center. The investigator or designee will review the laboratory report within 24 hours (except during clinic holidays, when review will be performed within 72 hours) after receipt of the results and assess the clinical significance of all abnormal values. Results must be reviewed prior to dosing and appropriate action taken for any clinically significant abnormal values. Values will be documented on the laboratory report until stabilized, or the laboratory value returns to a clinically acceptable range (regardless of relationship to study medication) or baseline. Any laboratory value that remains abnormal at the end-of-study (EOS) and that is considered clinically significant will be followed according to

accepted medical standards for up to 30 days or until resolution of the abnormality or return to baseline.

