#### Table 6.3Part 1 and 2: Schedule of Assessments and Procedures

		Da	Cycle 1 y 1 through	21	Day	Cycle 2 22 through	42	Cycle 3-X 21 day cycles, visit on 1 st day of cycle	
Visit	1 Screening	2 Baseline	3 Tx	4 Tx	5 Tx	6 Tx	7 Tx	8 -X Tx	Final Study Visit/ Early Discontinuation
Visit Day	-28 to -1	$1\pm 0$	$8 \pm 1$	$15 \pm 1$	$22 \pm 1$	$29 \pm 1$	$36 \pm 1$	43 ± 1	
Electrocardiogram (ECG) j	Х		Х						
Adverse events (AEs)		Х	Х	Х	Х	Х	Х	Х	Х
Compliance by pill count			Х	Х	Х	Х	Х	Х	Х
Obtain unused drug			Х	Х	Х	Х	Х	Х	Х
ECHO cardiogram or MUGA	Х								

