#### Table 6.3Part 1 and 2: Schedule of Assessments and Procedures

Table footnotes:

a Full medical history at screening, review/update of history only at subsequent visits.

b Ophthalmological examinations will be performed by an ophthalmologist at screening, at study termination and if clinically indicated.

c ONLY if the screening serum pregnancy test was performed more than 1 day previously.

d After screening and baseline, urine pregnancy test which if positive, confirm with serum test.

e Study drug to be taken twice daily, first dose in clinic on days when PK sampling occurs i.e., Cycle 1 on Visit 2 (Day 1) and Visit 5 (Day 22), remaining doses on all other days to be self-administered by patient.

f PK blood samples will be collected prior to first morning dose and at 0.5 hours, 1 hour, 2 hours, 4 hours, 6 hours, 8 hours and 12 ±2 hours post-dose. Pharmacodynamic and PBMC blood samples will be collected prior to first morning dose and at 4 hours post-dose.

g Pharmacodynamic, PK, and PBMC blood samples are required at baseline where feasible. Additional biomarkers and DNA sequence analysis may be identified and measured as appropriate by collection of whole blood prior to dosing initiation and after drug levels have reached steady-state. Leukemic cell genotyping by DNA analysis may be performed to identify somatic alterations, relying on either available stored samples or freshly collected samples.

h Bone marrow aspirate and/or biopsy. Peripheral, Geimsa and Iron stained slides to be provided with each bone marrow aspirate or biopsy. Bone marrow cytogenetics (cytogenetics should include at least 20 clones). Bone marrow aspirates may be used to evaluate biomarkers of drug response.

i Chemistry (to include calcium and inorganic phosphorus), hematology and urinalysis. After Cycle 2, clinical chemistry (to include calcium and inorganic phosphorus), hematology and urinalysis may be performed once per cycle or more frequently at the investigator's discretion.

j Patients with a normal ECG in Cycle 1 need not have repeat ECGs in subsequent cycles. Patients should be supine for 5 minutes prior to the ECG.

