#### 10 SAFETY

Safety analyses will be performed using the Safety Population. Safety will be assessed by examining all adverse events reported during the study including the incidence, and relationship to BVD-523. In addition, safety evaluations will be conducted at Baseline, Days 1, 8, 15, 22, 29, 36, 43, and, in subjects who continue treatment, every 3 weeks or if clinically indicated thereafter. These evaluations will include a targeted ECG where clinically warranted, and clinical laboratory analytes (hematology, chemistry, urinalysis and pregnancy test). An ophthalmologic assessment will also be conducted at baseline, at the end of study and at other visits by an ophthalmologist if clinically indicated.

\*Added as a response option in Note to File dated 21JUL2015

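### The only scheduled on-treatment ECG (Day 8) has no set or recorded time relative to the dose, so a null QTcF result would be hard to interpret; wording that makes ECGs conditional also needs reconciling

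*Protocol*

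**What the plan says.** Protocol Section 1.5.1 (QTc Prolongation) describes a "low, but observable, potential to cause QT prolongation" and commits to a check: "QTc assessment will be performed at baseline and on Day 8, at steady state". Table 6.3, and its copy in SAP Section 3.2, mark an ECG at Screening and at Visit 3 (Day 8 ± 1) and at no other visit. Section 5.2.3 gives the Day 8 instruction as "Obtain a 12-lead ECG". SAP 10.6 likewise has every subject measured at Screening and on Cycle 1 Day 8, and summarises the parameters, QTcF among them, by dose and time point.

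Footnote j of Table 6.3 asks for five minutes supine and says nothing about time since dose. Footnote e places in-clinic dosing on the PK days, Day 1 and Day 22; on other days patients dose themselves. Footnote f gives clock times after dose for the PK samples and fixes the PD and PBMC post-dose samples at 4 hours.

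Two general paragraphs are worded differently. Protocol 6.5 lists Day 8 among the safety evaluation days but includes "electrocardiography in subjects where clinically indicated and clinical laboratory studies". SAP 10 lists the same days and has a "targeted ECG where clinically warranted".

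After Cycle 1, footnote j states: "Patients with a normal ECG in Cycle 1 need not have repeat ECGs in subsequent cycles". Section 5.4.1 repeats this and asks for an ECG from Cycle 3 on only if appropriate. Sections 3.1.2 and 3.1.3 allow a patient's dose to be escalated after one completed cycle.

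**The concern.** The Day 8 ECG is the plan's own QTc check, and it is the one exposure-dependent measurement in Cycle 1 without a time after dose. The patient takes the Day 8 dose without supervision and no PK sample is drawn that day, so there is neither a nominal time nor a concentration to place the reading within the dosing interval. Readings near peak and near trough would enter the same Day 8 row. If that row shows no QTcF change, the analyst cannot tell a drug without effect from readings taken at low exposure.

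Two inconsistencies add to this. A site following Protocol 6.5 could treat the Day 8 ECG as optional. And a patient with a normal Cycle 1 ECG who is then escalated has no scheduled ECG at the higher dose, although SAP 10.6 reports ECGs by dose.

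**Working it through.** **Is the Day 8 ECG timed anywhere?** The places that could set a time are Section 1.5.1, Section 5.2.3, Table 6.3 with footnote j, SAP Table 3.1, SAP 7.1 and SAP 10.6. None does. The SAP 7.1 window for this visit is study days 7 to 9, with no within-day element.

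**Is Day 8 at steady state?** Yes, if dosing is uninterrupted. The protocol's own criterion is 5 days or 10 consecutive doses. Five days is 120 h, which is 120/4 = 30 to 120/2 = 60 half-lives at 2 to 4 h, and still 120/12 = 10 at 12 h. The gap concerns time within the dosing interval only.

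**How much can exposure vary within the interval?** The plan states no figure to reproduce, so this is a sizing under assumptions.

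Inputs:
- Dosing interval τ = 12 h (Section 8.1.2 allows ± 2 h).
- Half-life: Section 1.5.3 says the compound "has a half-life of 2-4 hours across all species", a preclinical figure from a suspension formulation. The documents give no human value, so 6, 8 and 12 h are added as assumptions.
- tmax: not given; 1, 2 and 4 h after a single dose are assumed.

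Model: one compartment, oral, at steady state, with k = ln 2 / half-life and ka solved from tmax = ln(ka/k)/(ka − k):

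C(t) ∝ e^(−kt)/(1 − e^(−kτ)) − e^(−ka·t)/(1 − e^(−ka·τ))

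Worked case, half-life 4 h and tmax 2 h: k = 0.173, ka = 1.10.
- Trough: 0.125/0.875 = 0.143; the second term is negligible.
- Peak, at about 1.85 h: 0.726/0.875 − 0.131 = 0.699.
- Ratio: 0.143/0.699 = 20.5%.

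Trough as a percentage of peak; in brackets, the share of the interval spent below half of peak:

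| Half-life | tmax 1 h | tmax 2 h | tmax 4 h |
|---|---|---|---|
| 2 h | 2.6% (73%) | 6.1% (58%) | not attainable with ka > k |
| 3 h | 8.6% (65%) | 12.9% (52%) | 36.7% (18%) |
| 4 h | 15.6% (57%) | 20.5% (45%) | 39.5% (15%) |
| 6 h | 28.7% (41%) | 33.5% (30%) | 47.6% (4%) |
| 8 h | 39.0% (24%) | 43.4% (14%) | 54.6% (0%) |
| 12 h | 53.2% (0%) | 56.7% (0%) | 64.6% (0%) |

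Trough is below peak in every case, but the size of the gap depends heavily on two quantities the documents do not give.

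**Conditional or required?** Required: Protocol 1.5.1, 5.2.3 and Table 6.3; SAP Table 3.1 and 10.6. Conditional, in paragraphs that name Day 8: Protocol 6.5 and SAP 10. Nothing states which governs.

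**The case against.** The strongest case against is that this study has no QT objective, the preclinical signal is described as low, and ECGs are summarised descriptively. Section 1.5.1 reports Holter monitoring in the first study with no clinically significant cardiac abnormality to date. Entry requires QTc below 470 ms, and further ECGs remain possible where judged appropriate. All of that stands and lowers the urgency. It does not make an untimed reading interpretable, and Table 6.3 schedules no Holter monitoring here.

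A reader might infer several stronger points that the documents do not support:

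- *That a pre-dose ECG sees at most one eighth of peak exposure.* Simple decline over 12 h at a 4 h half-life gives 0.5^(12/4) = 12.5%, but that counts from peak. A pre-dose ECG is 12 h after the dose, hence less than 12 h after peak. The permitted 10 h interval alone gives 0.5^(10/4) = 17.7%, and the table goes higher.
- *That the ECG will miss a QTc effect.* Nothing says the Day 8 reading is likely to be at trough, no concentration-QTc relation is given, and a delayed or metabolite effect need not follow the parent drug's peak.
- *That the Day 8 ECG is optional.* It is unconditional wherever it is scheduled. The two looser paragraphs are general and may be meant for additional ECGs, which is why the fault is an inconsistency.
- *That dose times are recorded nowhere.* The eCRF and study manual are not available, and the SAP plans a dose history listing (16.2.5.3). What can be said is that neither document requires the time of the last dose to be recorded with the Day 8 ECG.
- *That the RP2D rests on this reading.* Protocol 3.1.4 bases the MTD on DLTs and allows PK, PD and cumulative toxicity to support the RP2D.

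**Conclusion.** The point holds as one of timing and interpretability. The plan's single scheduled on-treatment ECG is not tied to the dose, so SAP 10.6 would pool QTcF readings across a 12 ± 2 h interval, and a null summary would be hard to interpret. Under the preclinical half-life of 2 to 4 h, trough would be about 3% to 21% of peak (assumed tmax 1 to 2 h) or about 37% to 40% (assumed tmax 4 h, half-life 3 to 4 h). At an assumed half-life of 12 h it would be about 53% to 65%, and the concern shrinks accordingly. These figures rest on a one-compartment model and on half-life and tmax values not known for patients from the documents.

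Separately, and whatever the half-life, two sets of passages need reconciling: the conditional against the required wording for the Day 8 ECG, and the footnote j waiver against intra-patient escalation with ECGs summarised by dose. The documents give no basis for stating here which monitoring rule should apply after escalation.

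**What to change.** 1. In Protocol 5.2.3, Table 6.3 footnote j and SAP 10.6, take the already scheduled Day 8 ECG in one stated post-dose window. The sponsor should choose the window from its own human PK data; Section 1.4 shows that such data exist. Arrange the visit around the patient's usual dose time, leaving the dosing instructions unchanged.
2. Record the clock times of the last dose and of the ECG on the eCRF, and have SAP 10.6 report QTcF by time since dose.
3. Reconcile Protocol 6.5 and SAP 10 with Protocol 1.5.1, 5.2.3 and Table 6.3 and with SAP 10.6, so that the status of the Day 8 ECG is the same throughout.
4. Reconcile the footnote j waiver and Section 5.4.1 with the escalation provisions in 3.1.2 and 3.1.3 and with the by-dose summary in SAP 10.6. The clinical content of that decision is for the sponsor and investigators.

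Items 1 and 2 add no ECG. The cost is less flexible scheduling of the Day 8 visit and two extra eCRF fields.
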